1 SYNOPSIS

Study Synopsis	
Title	PREVENT ion of Non-Surgical Bleeding by Management of HeartMate II Patients without Antiplatelet Therapy
Acronym	PREVENT II
Objectives	Reduce the incidence of non-surgical bleeding in HeartMate II (HM II) patients without increasing the risk of thromboembolic (TE) events
Primary Hypothesis	HM II patients managed with warfarin alone (Treatment Arm) have a lower rate of non-surgical bleeding and an equivalent rate of stroke and TE events compared to patients managed with warfarin + acetylsalicylic acid (aspirin, ASA) together (Control Arm)
Primary Endpoints	
A comparison between the Treatment and Control Arms of:
 
Primary Efficacy Endpoint (Superiority): Composite incidence of non-surgical bleeding at 6 months post initial implantation, including but not limited to gastrointestinal (GI), genitourinary (GU), epistaxis, subdural hematoma, and primary hemorrhagic stroke (not due to ischemic conversion, or to treatment of a hemolysis/suspected thrombosis event)
 
Primary Safety Endpoint (Non-Inferiority): Composite incidence of pump thrombosis and TE stroke at 6 months post initial implantation, including ischemic stroke, or hemorrhagic stroke due to an ischemic conversion/treatment of an hemolysis/pump thrombosis event

Descriptive Endpoints	
Comparison between the Treatment and Control Arms in the rates of:
 
 • Overall bleeding • GI bleeding • Suspected and confirmed pump thrombosis • Stroke (ischemic and hemorrhagic) • Hemolysis (major and minor) • As treated analysis of anticoagulation and antiplatelet medications • Survival • Assessment of adherence to the PREVENT study recommended practices

Clinical Investigational Plan

Study Synopsis

Design

PREVENT II is a prospective, multi-center, randomized, double-blind placebo controlled study.

The randomization scheme will be 1:1, with a total sample size of 350 subjects, with 175 subjects in the Treatment Arm and 175 subjects in the Control Arm defined as:

- Treatment Arm: Warfarin (INR Target 2.0-2.5, median 2.25, per standard of patient care) + placebo (1 pill/day)
- Control Arm: Warfarin (INR Target 2.0-2.5, median 2.25, per standard of patient care) + acetylsalicylic acid (ASA) therapy (81mg/day)

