Maximum follow-up duration per subject will be 12 months. Primary endpoints will be evaluated at 6 months. Individual components of the primary endpoints along with the descriptive endpoints will be evaluated at 12 months.

Clinical Investigational Plan

Study Synopsis

Statistical Considerations	
Primary Efficacy Endpoint Analysis – Reduction of Bleeding: The rate of non-surgical bleeding at 6 months will be compared between the Treatment and Control Arms utilizing the Fisher’s Exact Test. The primary endpoint for efficacy will be assumed to be met if the p-value < 0.05. The assumption is that there will be a 15% rate reduction at 6 months.
 
A sample size of 330 subjects (165 in each arm) with an alpha of 0.05 will provide 80% power to demonstrate a significant difference between the Treatment and Control Arms.
 
Primary Safety Endpoint Analysis – Non-Inferiority of Stroke and Thrombus: The difference in the rates of the composite endpoint of stroke and pump thrombosis between Treatment and Control Arms and the 95% confidence limit of the difference will be evaluated. If the upper confidence limit of the difference is < 10% then the non-inferiority criterion will be considered to have been met.
 
A sample size of 338 subjects (169 in each arm) will provide 80% power, with a target alpha of 0.025 (because this will be a one-sided test on the upper confidence limit) to demonstrate non-inferiority of the Treatment Arm to the Control Arm.
 
A total study sample size of 350 subjects will provide enough statistical power to demonstrate both efficacy and safety of the warfarin only anticoagulation regimen in these patients.
 
Both primary endpoints must be met for the study to be successful.
 
Intermediate Safety Assessment: A safety assessment will be performed after 60 subjects have completed 3 months of follow-up. Both incidence of stroke and pump thrombosis will be analyzed and results will be presented to the Steering Committee. Additionally, after the initial 3-month safety review, an analysis of AEs associated with primary endpoints will be presented to the Steering Committee for continued safety assessment in regular 6-month intervals. The Steering Committee will review the findings and make a decision to proceed or stop the study due to safety concerns.

Devices Used	HM II Left Ventricular Assist Device (LVAD)

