2.2 THROMBOSIS IN HM II PATIENTS

Despite bleeding being the more common adverse event, consequences of thrombosis can be far more serious. Early HM II clinical experience demonstrated a low rate of pump thrombosis and stroke (1, 2, 7, 14), but over time changes in management practices to address bleeding events have partially contributed to an increasing risk of pump thrombosis in HM II patients (22). Starling *et al.* reported an alarming increasing incidence of HM II pump thrombosis from 2.2% before 2011 to 8.4% after 2011 (23). Despite the alarming trend, there was significant disparity and center-to-center variability in the reported rates of pump thrombosis. For example, an analysis of clinical experience from 7 centers (24) showed that the risk of early pump thrombosis was found to be much lower (3.9%) compared to the published clinical experience (23, 25). In addition, subsequently published letters to the editor suggested that the increases in pump thrombosis rates observed in some centers were not evident at all HM II centers (26, 27).

Due to the variability in pump thrombosis rates and patient management practices, the PREVENT study (PREVENTion of HeartMate II Thrombosis through Clinical Management; ClinicalTrials.gov identifier: NCT02158403) was developed to investigate a set of recommended practices (**Appendix C**) based on the HM II instructions for use (IFU) with modifications derived from clinical practice (28). PREVENT evaluated the rate of pump thrombosis in HM II patients when the recommended practices were adopted across centers to minimize center-to-center variability and standardize clinical management.

Primary endpoint results from the PREVENT study were recently presented at the International Society of Heart and Lung Transplantation (ISHLT) 2016 annual meeting, where the rate of early (≤ 3 month) pump thrombosis was demonstrated to be 2.9% (significantly lower than the published rate of 8.4% at 3 months) (29). The reduction in the early risk of pump thrombosis associated with the adoption of consistent patient management techniques, has been confirmed by other studies (30, 31). Furthermore, an analysis of PREVENT data revealed that a sub-group of patients (~20% of the enrolled patient population) were not on ASA or any antiplatelet therapy; these patients did not experience any of the pump thrombosis events captured as part of the primary endpoint.

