4.2 STUDY DESIGN AND SCOPE

This study is a prospective, multi-center, randomized, double-blind placebo-controlled study of subjects receiving the HM II LVAD as per currently approved indications for use. This is a post-market clinical study of HM II patient management practices to be conducted in the United States and Canada.

Subjects will be randomized in a 1:1 fashion to the following research drug groups:

- 1) Treatment Arm: Warfarin (INR target: 2.0-2.5, median: 2.25) + Placebo (1 pill/day)
- 2) Control Arm: Warfarin (INR target: 2.0-2.5, median: 2.25) + ASA Therapy (81mg/day)

The study will investigate if subjects in the Treatment Arm experience a reduced incidence of non-surgical bleeding, without an increased risk of TE events.

Once randomized, subjects will be placed on the research drug (ASA therapy or placebo) no later than post-operative day (POD) 5, provided bleeding has subsided and the subject is hemodynamically stable.

If the subject is experiencing bleeding or is not hemodynamically stable by POD 5, the subject must start the study drug as soon as bleeding has subsided and hemodynamic stability has been achieved, but no later than POD 15. If administration of the research drug has not begun by POD 15, the subject will be withdrawn from the study.

Withdrawn subjects will not be replaced.

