4.4 OBJECTIVE

The primary objective of the study is to reduce the incidence of non-surgical bleeding in HM II patients, without increasing the risk of TE events, by eliminating ASA therapy from the antithrombotic management regimen for HM II patients. The primary objective will be accomplished by a comparison of non-surgical bleeding and TE events at 6 months post initial implantation between the Treatment and Control Arms.

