12.1.5 PRIMARY SAFETY ENDPOINT

Assumptions: Based on the analysis of the first 100 subjects enrolled in the PREVENT study (Data on file), the anticipated composite incidence of TE events in the Control Arm at 6 months is expected to be 8%. The assumption for PREVENT II is that the Treatment Arm will experience an incidence of TE events of no more than 9% at 6 months. The Treatment Arm will be considered non-inferior to the Control Arm if the upper one-sided 95% confidence limit of the risk difference in the 6 month TE rate between research drug arms (Treatment - Control) is less than +10% ("positive 10%", where 10% is the non-inferiority Δ in the above null and alternative hypotheses).

A sample size of 338 subjects (169 each in the Treatment and Control Arms) will achieve 80% power to prove the Treatment Arm is non-inferior to HM II when the margin of non-inferiority is 10% ($=\Delta$ in the above null and alternative hypotheses) using the Farrington-Manning risk difference approach to non-inferiority at a one-sided alpha = 0.025.

[figure not shown]

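### The hypothesis and objectives speak of an equivalent TE rate and no increased risk, but passing the 10-point non-inferiority test excludes only a true Treatment rate of about 18% or more against 8%

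*Combined protocol and SAP*

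**What the plan says.** Several places describe the safety conclusion that the trial aims for:

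- Synopsis, Primary Hypothesis: Treatment is said to have "an equivalent rate of stroke and TE events compared to patients managed with warfarin" plus aspirin.
- Synopsis, Objectives: bleeding is to be reduced "without increasing the risk of thromboembolic (TE) events".
- Section 4.2: the study asks whether Treatment Arm subjects "experience a reduced incidence of non-surgical bleeding, without an increased risk of TE events".
- Section 4.4: the aim is to reduce bleeding "without increasing the risk of TE events, by eliminating ASA therapy".

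The decision rule is different in kind. In the Synopsis: "If the upper confidence limit of the difference is < 10% then the non-inferiority criterion will be considered to have been met". Section 12.1.5 repeats the margin, stating its power "when the margin of non-inferiority is 10" percentage points. It expects 8% in Control, assumes no more than 9% in Treatment, and sizes the test at 169 per arm for 80% power by Farrington-Manning at one-sided 0.025. The same section states the decision limit as a one-sided 95% limit. It gives a source for the 8% but no reason for the 10 points. The Synopsis adds that 350 subjects give enough power to show both efficacy and safety.

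**The concern.** A one-sided non-inferiority test can support one statement: the true excess is smaller than the margin. It cannot support equivalence, which would need limits in both directions and a narrow band. Nor can it support absence of increase, which would need an upper limit at or below zero. Here the margin is larger than the Control rate it is added to, so the gap between the wording and the test is wide. A reader who takes the hypothesis and objectives at face value after a pass would believe that dropping aspirin adds no TE risk. The data would have shown only that the risk is not 10 or more points higher. Section 2.4 expects the results to influence the care of thousands of patients, so the wording of the claim matters.

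**Working it through.** **Inputs.** Control 8%, Treatment 9%, margin 10 points, Farrington-Manning, one-sided alpha 0.025, 169 per arm (Section 12.1.5); planned enrolment 350, 175 per arm (Synopsis, Design). Both error levels written in Section 12.1.5 are carried through. The direction of the test is taken from the decision rule there.

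**1. The plan's sample size.** n per arm = [(z(0.975)·s0 + z(0.80)·s1) / (0.10 − 0.01)]².

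- The restricted estimates under the null are 0.1545 and 0.0545, so s0 = √(0.1545·0.8455 + 0.0545·0.9455) = 0.4269.
- s1 = √(0.09·0.91 + 0.08·0.92) = 0.3943.
- n = [(1.960·0.4269 + 0.8416·0.3943) / 0.09]² = 168.6, rounded up to 169 per arm, 338 in all.

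The stated figure reproduces. One-sided 0.05 would give 132 per arm, so the plan was sized at 0.025.

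**2. What a pass excludes.** 8% + 10 points = 18%, and 18/8 = 2.25. This is a bound on the true rate, not an observed rate that could pass.

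**3. Largest observed excess that passes.** Take 175 per arm and 14 Control events (8.0%), with z = (pT − pC − 0.10)/SE and the SE from the restricted estimates.

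- 20 Treatment events (11.4%): restricted estimates 0.1605 and 0.0605; SE = √[(0.1605·0.8395 + 0.0605·0.9395)/175] = 0.0331; z = −0.0657/0.0331 = −1.99. This is beyond −1.96, so it passes at 0.025.
- 21 events (12.0%): z = −1.80. It fails at 0.025 and passes with a one-sided 95% limit (−1.645).
- 22 events (12.6%): z = −1.62. It fails at both levels. A simple Wald one-sided 95% limit would let it pass.

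For 20 against 14, the risk ratio is 20/14 = 1.43. The SE of its log is √(1/20 − 1/175 + 1/14 − 1/175) = 0.332, giving a 95% CI of 0.75 to 2.74.

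**4. Chance of passing.** Exact binomial enumeration of the Farrington-Manning test, 175 per arm, true Control rate 8%:

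| True Treatment rate | One-sided 0.025 | One-sided 95% limit |
|---|---|---|
| 9% | 83% | 90% |
| 10% | 71% | 82% |
| 11% | 58% | 70% |
| 12% | 44% | 57% |
| 13% | 31% | 44% |
| 14% | 21% | 32% |
| 16% | 8% | 14% |
| 18% | 2.4% | 5.1% |

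A true rise by half (8% to 12%) therefore passes in roughly half of trials.

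**The case against.** The best defence is that the operative text is sound. The endpoint is labelled non-inferiority, the rule says non-inferior, and the success statement requires only that both endpoints be met, without either disputed phrase. Sections 4.2 and 4.4 state a question and an aim, and Section 3 openly says that Treatment subjects may be at increased TE risk. Section 12 already plans risk ratios for adverse events. All of this stands, and it confines the fault to the hypothesis, objective and design wording. It does not remove it: the primary hypothesis asserts equivalence, the Synopsis promises to show safety, and no relative measure is specified for the 6-month composite.

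Three stronger readings are tempting but unsupported.

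- A reader might infer that the trial could show a clear TE increase and still succeed. At the planning rate it could not: 20 against 14 has a risk ratio interval that includes 1 (Fisher p = 0.37). With Control at 8% and a true excess of 3 to 6.2 points, the chance of both passing and showing a significant excess (two-sided Fisher p < 0.05) is at most about 1 in 900,000 at one-sided 0.025, or 5 in 100,000 with the one-sided 95% limit.
- A reader might infer from the "alarming increasing incidence of HM II pump thrombosis from 2.2% before 2011 to 8.4% after 2011" (8.4 − 2.2 = 6.2 points) that 10 points is too wide by the protocol's own standard. That figure is a calendar-time change in one component, and Section 2.2 later treats the 8.4% as a 3-month rate. It does not calibrate a randomized contrast on a 6-month composite.
- A reader might infer that the margin or sample size is an error. The sample size is right. The margin is a trade-off: at 175 per arm, a 6.2-point margin would cut power for 9% against 8% from 83% to 39%, and 80% power at 6 points would need 511 per arm.

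**Conclusion.** The point holds as a mismatch between the stated conclusion and the test. At the planning Control rate, a pass excludes a true Treatment rate of about 18% or more and nothing smaller. A true 12% against 8% passes 44% to 57% of the time, depending on which of the two stated error levels governs. The largest passing excess against 14 Control events, 3.4 to 4.0 points, would be neither established nor excluded as a real increase.

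These figures assume 175 evaluable subjects per arm, a true Control rate of 8% and the Farrington-Manning test. The 18% and the ratio of 2.25 move with the Control rate; with a lower rate the fixed margin is looser in relative terms. The discrepancy between the two error levels is a separate matter that shifts the pass probabilities but not the 18%.

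**What to change.** Keep the test, the margin and the sample size.

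1. In the Synopsis (Objectives and Primary Hypothesis), Section 4.2 and Section 4.4, replace the claims of equivalence and of no increased risk with: non-inferior, meaning that an absolute increase of 10 percentage points or more in 6-month TE incidence is excluded (18% against 8% at the planning rate).
2. Qualify in the same way the Synopsis sentence that says 350 subjects suffice to show efficacy and safety.
3. Pre-specify that the risk ratio and its 95% CI for the 6-month safety composite are reported beside the risk difference wherever non-inferiority is stated. This extends the adverse-event risk ratios already planned in Section 12.

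The cost is a less favourable claim and one extra estimate. No subjects, visits or data are added.

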12.2 ADDRESSING CLINICAL SCENARIOS IN WHICH CHANGES TO ANTIPLATELET THERAPY MAY BE REQUIRED

Subjects should be maintained on both Warfarin (with a target INR: 2.0-2.5) and the research drug (ASA or placebo) for the entire duration of the study. Changes in therapies are only accepted under the following scenarios:

Clinical Investigational Plan

[figure not shown]
Figure 3 – Treatment of Non-Surgical Bleeding Events

Clinical Investigational Plan

[figure not shown]
Figure 4 – Treatment of Thromboembolic Events

Clinical Investigational Plan

[figure not shown]
Figure 5 – Treatment of Hemolysis Events

Clinical Investigational Plan

Figure 6 – Treatment of Transient Ischemic Attack Events

Clinical Investigational Plan

12.2.1 PERSISTENT CHANGES TO ANTIPLATELET THERAPY

If the investigator persistently deviates from the CIP by deliberately changing antiplatelet therapy outside of the scenarios outlined above, the subject will be censored from that point onwards. Follow-up will continue, but the data will not contribute to the primary endpoints. This will be considered a CIP deviation and may result in site disqualification. The deviation and details about therapy changes will be recorded on the appropriate CRF.

12.3 SAFETY ASSESSMENT

A safety assessment will be performed after 60 subjects have completed 3 months of follow-up. Both incidence of stroke and pump thrombosis will be analyzed. Results will be presented to the Steering Committee, which will review the findings and make a decision to proceed or stop the study due to safety concerns. Enrollment will continue during this review process. Additionally, after the initial 3-month safety review, an analysis of AEs associated with the primary endpoints will be presented to the Steering Committee for continued safety assessment at regular 6-month intervals. The Steering Committee will review the findings and make a recommendation to proceed or stop the study due to safety concerns.

12.4 RANDOMIZATION APPROACH

Subjects will be randomized in a 1:1 fashion (one Treatment Arm subject to one Control Arm subject). The randomization will be stratified by study site and blocked to maintain the 1:1 ratio over time. The Sponsor will implement randomization through ALMAC Clinical's WebEZ system. Randomization will occur after the subject is successfully implanted with the HM II, and must be completed within 48 hours of implant.

13 DOCUMENT MANAGEMENT AND RETENTION

13.1 REGULATORY DOCUMENTATION

The following study documents will be maintained by the study site and copies of site-specific documents sent to Sponsor (including but not limited to):

- Research Agreement and amendments
- Approved Protocol and amendments
- Protocol signature page
- IRB approved ICF templates
- IRB Submissions and Approval(s)
- IRB Membership Roster(s) or Federal wide Assurance (FWA) number
- Pertinent IRB Correspondence
- Delegation of Authority Log
- Training Log
- Financial Disclosure(s)
- Curriculum Vitae(s)
- Medical License(s)
- Laboratory Certifications and Normals
- Screening Log
- Aspirin Resistance Testing Instructions
- WebEZ Instructions
- Drug Return Instructions (DRI)
- Research Drug Shipping/Receiving Receipts
- Submission of Media Instructions
- Media Shipping/Receiving Receipts
- Monitoring Log
- Sponsor Correspondence

Clinical Investigational Plan

- Source documentation (such as subject clinic charts, medical records, laboratory records)
- Notes to File

13.2 RETENTION OF RECORDS

The PI will maintain all study documents from prior, during, and (as specified) after the clinical study on file at the site for a minimum of 15 years after the termination of this study, or longer as per local laws, or when it is no longer needed to support a marketing application, whichever is later.

The PI must contact the Sponsor prior to destroying or archiving off-site any records and reports pertaining to this study to ensure that they no longer need to be retained on site.

All original subject files must be stored for the longest possible time permitted by the regulations at the hospital, research institute, or practice in question. If archiving can no longer be maintained at the site, or if the responsibility of retention transfers to a different individual, the investigator will notify the Sponsor.

All data and documents will be made available on request of the relevant authorities in case of an audit. In the event of an audit by the FDA or other regulatory authority, the PI must notify the Sponsor.

The Sponsor will archive and retain all essential clinical study documents from prior, during and (as specified) after the clinical study as per requirements.

14 STUDY COMMITTEES

At least two committees will be established as part of this study: the Steering Committee and the Clinical Events Committee (CEC).

The Steering Committee will oversee the conduct and execution of the study. The Steering Committee, already established, is comprised of three cardiologists and two cardiovascular surgeons, who are each leaders in the field of MCS therapy for advanced heart failure. The Steering Committee will meet regularly to discuss study progress and proceedings of the meetings will be documented. See Section 12.3 for additional information on the Steering Committee's safety assessment of trial progress. The responsibilities of the Steering Committee may include, but are not limited to:

- Reviewing and providing input to the study design, and the study protocol
- Providing assessment of perceived evidence gaps and opinions of the medical community regarding study design and execution
- Providing guidance on study execution including study eligibility questions, data analysis, presentation/publication of study results, patient safety, and address any study-related issues (e.g. recruitment and compliance to study protocol)
- Provide recommendations for the selection of other committee members, including the Publication Committee, the CEC, and other sub-committees

The CEC will be responsible for the adjudication process for adverse events that are related to bleeding and thromboembolic events. The CEC will be established prior to study

Clinical Investigational Plan

initiation, and will meet regularly to ensure that adverse events reported as part of the study are adequately adjudicated.

